11.6.2.3 Questionnaires

11.6.2.3.1 Urge-to-Smoke Questionnaire of Smoking Urges Brief

The total score and the two factors from the QSU-brief will be listed for all scheduled time points and summarized overall and by the two stratification factors (sex, mCC nicotine level at Admission) for the PK population, as specified in Section 11.1.1 “Stratified Presentation”. This will also be done for the changes from baseline, the percent change from baseline and the maximum percent decrease over time. The percent change and the time to maximum percent decrease in total score will be summarized by product and analyzed using the Hodges-Lehmann method. The individual responses to all questions will be listed by product, study day, and assessment time points.

In addition line graphs will be produced for the total score and factors means (and 95% CI) over all timepoints.

The analysis of the subjective effects of smoking (the total score, and Factor-1 and Factor-2 from the QSU-brief) will be performed using the same mixed effects ANOVA

adopted for the analysis of CO breath test described in Section 11.6.2.2.1 “Exhaled CO and COHb”, including also the baseline score.

The main comparison will be the mean difference over all timepoints. LS means for each product, the overall mean difference and the mean differences at each time point will be presented in the tables as a point and interval (95% CI) estimate. Figures of the LS mean difference and 95% CI at each time point will be produced.

The data will be presented in the below outputs:

TFL number	Title
TABLES	
15.2.4.11	Analysis of QSU-brief Questionnaire Factors and Total Score – PK Population
15.2.4.12	Analysis of the Time to Maximum Percent Decrease in Total Score – PK Population
15.2.4.13	Descriptive Statistics of QSU-brief Questionnaire Factors and Total Score – PK Population
15.2.4.13.1	Descriptive Statistics of QSU-brief Questionnaire Factors and Total Score by Sex – PK Population
15.2.4.13.2	Descriptive Statistics of QSU-brief Questionnaire Factors and Total Score by Nicotine Level – PK Population
15.2.4.14	Descriptive Statistics of Time to Maximum Decrease in Total Score – PK Population
15.2.4.14.1	Descriptive Statistics of Time to Maximum Decrease in Total Score by Sex – PK Population
15.2.4.14.2	Descriptive Statistics of Time to Maximum Decrease in Total Score by Nicotine Level – PK Population
FIGURES	
15.1.2.9.1	QSU-brief Factors and Total Score Profiles Arithmetic Mean and 95% CI PK Population
15.1.2.10.1	QSU-brief Factors and Total Score Profiles Arithmetic Least Squares Mean Differences and 95% CI –PK Population
LISTINGS	
15.3.6.11	Listing of QSU-brief Questionnaire Results

11.6.2.3.2 Modified Cigarette Evaluation Questionnaire

The MCEQ domain scores composed of the three multi-item subscales and two single items from the MCEQ will be listed and summarized overall and by the two stratification factors (sex, mCC nicotine level at Admission) for the PK populations, as specified in Section 11.1.1 “Stratified Presentation”. The individual responses to all questions will be listed.

A mixed effects ANOVA model will be used to estimate mean CHTP 1.1 M - mCC differences of the MCEQ domain scores and variances, with a REML method (Bethesda,

2013; Brown and Prescott, 1999). Subjects within sequence will be used as random effects and fixed effects are period, sequence, and product exposure.

```
Proc mixed data=_data_ method=reml maxiter=200;
Class subject sequence product period;
Model response = sequence period product;
Random subject(sequence);
Lsmean product / pdiff =control('mCC') alpha=0.05 cl;
Run;
```

LS means for each product and the overall point and 95% interval estimate of the difference will be presented in the tables.

The data will be presented in the below outputs:

TFL number	Title
TABLES	
15.2.4.15	Analysis of MCEQ Subscales – PK Population
15.2.4.16	Descriptive Statistics of MCEQ Subscales – PK Population
15.2.4.16.1	Descriptive Statistics of MCEQ Subscales by Sex – PK Population
15.2.4.16.2	Descriptive Statistics of MCEQ Subscales by Nicotine Level – PK Population
LISTINGS	
15.3.6.12	Listing of MCEQ Questionnaire Results

11.6.3 Supportive/Sensitivity Analysis

To better understand the impact of the higher than expected T_0 values, an analysis of the PK parameters will be performed as described above, however the data for subjects with their T_0 value $>5\%$ of their C_{max} value will be excluded from the analysis. To support the interpretation of the PK analysis, the values of nicotine concentration greater than BLOQ before T_0 will be listed together with any PK parameters excluded from the analysis. Listings will be presented by PK parameter, sequence, period and study date.

Sensitivity analysis will be conducted on the C_{max} and $AUC_{(0-last)}$ endpoints for the PK population should there be 20% or more missing PK parameter values. This analysis is conducted on all the available PK parameters and subjects will be excluded from the analysis if 20% or more of their PK parameter values are missing. The analysis will be conducted in the natural log scale using mixed effects ANOVA model including period, sequence, and product exposure as fixed effects and subject within sequence as a random effect. Point and 95% interval estimates of the ratios will be back-transformed by exponentiation and tabulated.

Sensitivity analysis will be conducted following the model described in 11.6.1 “Primary Analyses” in case of missing data as described in Section 11.1.5 “Handling of Dropouts or Missing Data (including outside the limits of quantification)”:

- 1) Where there is a missing sample taken at 1 h post-exposure or later and in the subsequent PK sample, nicotine is not quantifiable (BQL) or the missing sample result occurs at 24 h post-exposure AUC_{0-last} will, as well as being analysed and reported as planned, have a sensitivity analysis excluding those subjects.
- 2) Where there is a missing sample before 1 h post-exposure the parameters C_{max} and t_{max} will, as well as being analysed and reported as planned, have a sensitivity analysis excluding those subjects who have a missing sample before 1 h post-exposure.
- 3) Where the sample for the $15 \text{ min} < T_0$ time point is missing AUC_{0-t} will, as well as being analysed and reported as planned, have a sensitivity analysis excluding those subjects who have a missing sample at the $15 \text{ min} < T_0$ time point.

In case any time information is imputed for the computation of PK parameters as described in Section 11.1.5 “Handling of Dropouts or Missing Data (including outside the limits of quantification)” in any PK population, the median t_{max} for CHTP 1.1 M will be calculated following the imputation of missing time data by 0 sec and 30 sec. If the difference between the two median t_{max} is larger than 5%, a supportive analysis will be conducted by repeating the analyses described in Section 11.6.1 “Primary Analyses” and 11.6.2.1 “Pharmacokinetics” on the t_{max} , $AUC_{(0-last)}$, and $AUC_{(0-t)}$ endpoints estimated by means of the imputation of missing time by 0 sec.

The data will be presented in the below outputs:

TFL number	Title
TABLES	
Table 15.2.4.2.1	Analysis of Pharmacokinetic Parameters of Nicotine: sensitivity analysis: missing data - PK Population
Table 15.2.4.2.2	Analysis of Pharmacokinetic Parameters of Nicotine: sensitivity analysis: quantifiable predose concentrations - PK Population
Table 15.2.4.2.3	Analysis of Pharmacokinetic Parameters of Nicotine: sensitivity analysis: missing concentrations – PK Population
Table 15.2.4.3	Analysis of Pharmacokinetic Parameters of Nicotine by Zero Sec Imputation – PK Population

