7.1.3 Criteria for Calculating the Apparent Terminal Elimination Half-Life

$t_{1/2}$ will be calculated according to the following formula:

$$t_{1/2} = \frac{\ln(2)}{\lambda_z}$$

where λ_z will be calculated by least squares (LS) linear regression of the terminal portion of the log-transformed plasma concentration-time curve.

The start of the terminal elimination phase for each subject will be defined by visual inspection and will be the first point at which there is no systematic deviation from the log-linear decline in plasma concentrations. The concentrations included in the terminal elimination phase will be flagged in the data listings.

Period of Estimation

- Apparent terminal (elimination) half-lives will be calculated, where possible, over at least 2 half-lives. Where an apparent terminal half-life is estimated over less than 2 half-lives, it will be flagged in the data listings.
- An apparent terminal half-life will not be reported if it can only be calculated over a period that is less than 1.5 half-lives.

Number of Data Points

- At least 3 data points with nicotine concentration greater than the LLOQ will be used for each subject in the regression analysis. An apparent terminal half-life will not be reported if derived from less than 3 data points.

Goodness of Fit

- When assessing apparent terminal phases, the coefficient of determination, R^2 adjusted value, will be used as a measure of the goodness of fit of the data points to the determined line. This parameter will be used as it is considered to be a better assessment of the goodness of fit, compared to R^2 , as it adjusts for the number of points included in the line therefore allowing for a more direct comparison between elimination phases determined using different numbers of data points.
- Apparent terminal half-life will only be calculated if the R^2 adjusted value of the regression line is greater than or equal to 0.7.

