10.3 PK Population

The PK population consists of all the randomized subjects who give informed consent, completed at least one of the single use Day 1 or Day 3, and for whom at least one PK parameter can be derived. Only subjects without major protocol deviations that impact evaluability of the data (see Section 10.5 “Protocol Deviations”) will be included in the PK analysis sets.

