11.1.5 Handling of Dropouts or Missing Data (including outside the limits of quantification)

For questionnaire data total scores and domain or subscale scores may use a certain degree of imputation (by averaging across individual item scores) as detailed in Section 7.3 “Questionnaires”.

In general, values below the lower limit of quantification (LLOQ) will be imputed using 0.5 x lower limit of quantification. For values above the upper limit of quantification (ULOQ), *i.e.*, preceded by a “>”, for example “>xx,” the numerical xx will be used for calculation and reporting in summary tables. The number and percent of values below LLOQ or above ULOQ will be presented in each summary table.

For the calculation of PK parameters, partial dates/times for PK assessments or T_0 will not in general be imputed. For time points recorded in the format hh:mm, instead of hh:mm:ss, the missing information on seconds will be imputed by 30 sec.

For PK concentration data:

- 1) Where there is a missing sample taken at 1 h post-exposure or later
 - and in the subsequent PK sample, nicotine is quantifiable the data will be analysed and reported as planned.
 - And in the subsequent PK sample, nicotine is not quantifiable (BQL) or the missing sample result occurs at 24 h post-exposure AUC_{0-last} will, as well as being analysed and reported as planned, have a sensitivity analysis excluding those subjects.
- 2) Where there is a missing sample before 1 h post-exposure the parameters C_{max} and t_{max} will, as well as being analysed and reported as planned, have a sensitivity analysis excluding those subjects who have a missing sample before 1 h post-exposure.
- 3) Where the sample for the 15 min < T_0 time point is missing AUC_{0-t} will, as well as being analysed and reported as planned, have a sensitivity analysis excluding those subjects who have a missing sample at the 15 min < T_0 time point.
- 4) Where a subject was withdrawn at the 1 h post-exposure or later sample time, the only parameters to be reported would be C_{max} , t_{max} and AUC_{0-t} . All other parameters would be presented as NC (Not calculated) since only a limited partial concentration-

time profile is available and it is not comparable with the same parameters calculated for the other subjects and products and would therefore not be included in the statistical analysis.

- 5) If a subject is withdrawn < 1 h post-exposure, all PK parameters will be presented as NC.

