11.6 Planned Statistical Analyses

11.6.1 Primary Analyses

The primary parameters C_{\max} and $AUC_{(0-\text{last})}$ will be listed and summarized as described in Section 11.1 “General Considerations” and subsections. In addition plots of the data versus product will be provided.

The primary analysis of C_{\max} and $AUC_{(0-\text{last})}$ will be performed on the natural log-transformed parameters using an analysis of variance (ANOVA) model with terms for sequence, subject nested within sequence, period and product as fixed effect factors (Senn, 2002, FDA, 2001, CHMP, 2010 and CHMP Appendix IV, 2011).

Carry-over effect will not be tested, as it cannot be statistically distinguished from the interaction between product and period in a 2x2 crossover design.

The SAS code to be used is shown below:

```
Proc glm data=_data_ ;  
Class subject sequence product period ;  
Model log_pk = sequence subject(sequence) period product ;  
Lsmean product / pdiff =control('mCC') alpha=0.05 cl ;  
Test h=sequence e=subject(sequence) ;  
Run ;
```

where “log_pk” is the the natural log-transformed PK parameter being analyzed.

Supportive analysis will be performed as described in Section 11.6.3 "Supportive/Sensitivity Analysis".

LS means for each product will be back-transformed by exponentiation and will be tabulated together with the ratio (CHTP 1.1 M : mCC) and 95% CI.

The geometric CV will also be presented as $CV(\%) = 100\sqrt{(e^{\text{MSE}} - 1)}$, where MSE is the mean square error of the fitted model residual.

Exploratory subgroup analyses will be conducted for the primary endpoints in the following planned subgroups: sex (male or female), mCC nicotine level at Admission (ISO nicotine level ≤ 0.6 mg and >0.6 to ≤ 1 mg) provided there are more than 4 subjects in each category.

In case of any nicotine levels at T_0 greater than 5% of their C_{\max} value being observed, a supportive analysis as described in Section 11.6.3 "Supportive/Sensitivity Analysis" of the primary endpoints will be performed as described above, where the data of these subjects with nicotine levels at T_0 greater than 5% of their C_{\max} value will be excluded from the analysis.

Supportive analysis will be performed as described in Section 11.6.3 "Supportive/Sensitivity Analysis" in order to evaluate the sensitivity of CHTP 1.1 M effect estimates to methods used for missing data by means of a mixed model approach, should there be 20% or more missing parameter PK values.

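### The missing-data mixed model in SAP 11.6.3 removes the one-period subjects it could add, and neither of its 20% rules has a stated denominator

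*SAP*

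**What the plan says.** The primary analysis (SAP 11.6.1) is an ANOVA on log Cmax and log AUC(0-last) "with terms for sequence, subject nested within sequence, period and product as fixed effect factors". The same section plans a supportive analysis "to evaluate the sensitivity of CHTP 1.1 M effect estimates to methods used for missing data by means of a mixed model approach" if 20% or more of the values are missing.

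Section 11.6.3 gives the details. The trigger concerns the two primary "endpoints for the PK population should there be 20% or more missing PK parameter values". On the data used it says "This analysis is conducted on all the available PK parameters", and the same sentence continues that "subjects will be excluded from the analysis if 20% or more of their PK parameter values are missing". The model has subject within sequence as a random effect.

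Three other sections bear on who is affected:
- Section 10.3 admits to the PK population a subject who "completed at least one of the single use Day 1 or Day 3", so one period is enough.
- Section 11.1.5 item 4 covers late withdrawal: "Where a subject was withdrawn at the 1 h post-exposure or later sample time, the only parameters to be reported would be" three named ones, namely AUC(0-t'), tmax and Cmax. The rest are marked NC (not calculated).
- Section 7.1.2 sets one minimum data requirement for calculating AUC.

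No section says whether either 20% is counted per endpoint, over several parameters, over subjects, or over planned or attended periods.

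**The concern.** When subject is a fixed effect, a subject with one period has a parameter that absorbs the single observation, so the subject tells us nothing about the product contrast. A random-subject model can use that observation through between-subject information. This is the main reason to put such a model beside the primary one as a missing-data check. A rule that first removes these subjects works against the purpose given in 11.6.1.

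Items 1 to 3 of 11.6.3 do not fill the gap, because they rerun the primary model with further exclusions. At stake is how the missing-data sensitivity table (15.2.4.2.1) is read: agreement with the primary ratio could be taken as robustness when the rule itself produced it. With no denominator, the analysed set also depends on a programmer's choice.

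**Working it through.** **Inputs.** 48 subjects, 24 per sequence; within-subject CV 60% for Cmax; drop-out 5% (SAP 6.1 and 8). Assumed, because the SAP does not give it: between-subject log SD of 0.3, 0.5 or 0.8.

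**The plan's own figure.** Within-subject log SD = sqrt(ln(1 + 0.6²)) = 0.5545. SD of a paired difference = 0.5545 × √2 = 0.784. The smallest n with at least 80% probability that the 95% half-width is at most ln 1.3 is 43 (unconditional) or 44 (conditional on coverage). 44/0.95 = 46.3, so 47, and 48 for equal sequences. The planned 48 reproduces.

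**Step 1: one period missing.** With k parameters over two planned periods, the missing share is k/(2k) = 50% for any k. This exceeds 20%, so the subject is removed.

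**Step 2: counted per endpoint.** A subject is 0%, 50% or 100% missing, so only complete pairs stay. Intercept, sequence, period and product then saturate the four sequence-by-period cell means. Both models give the log ratio as half the difference between the sequences' mean period-1 minus period-2 differences. The ratios are therefore identical.

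Simulation confirms this (20 of 48 subjects lose one period at random, 2,000 runs per SD). The estimates agree to below 1e-15 in every run. The SEs are equal in 88% / 99% / 100% of runs at between-subject SD 0.3 / 0.5 / 0.8; they differ only when the between-subject variance is estimated as zero.

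**Step 3: pooled over parameters.** Table 3 lists 11 parameters (22 values over two periods), 11.6.1 plus 11.6.2.1 list 10 (20 values), and 5.1 plus 5.2 list 7 (14 values). Pooling the two primary parameters alone gives 4 values.

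| Event in one period | of 22 | of 20 | of 14 | of 4 |
|---|---|---|---|---|
| Whole period missing | 50% | 50% | 50% | 50% |
| AUC minimum (7.1.2) not met | 5/22 = 22.7% | 5/20 = 25% | 4/14 = 28.6% | 1/4 = 25% |
| Withdrawn at 1 h or later, period 2 | 8/22 = 36.4% | 7/20 = 35% | 4/14 = 28.6% | 1/4 = 25% |
| Terminal phase fails 7.1.3 | 4/22 = 18.2% | 4/20 = 20.0% | 2/14 = 14.3% | 0 |

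Row 2 loses every AUC and, where listed, the extrapolated percentage. Row 3 assumes that NC counts as missing; the subject has both Cmax values and is still dropped on every list. Row 4 assumes that a failed terminal phase makes all lambda_z-dependent parameters missing. That subject has complete Cmax and AUC(0-last), and is kept or dropped according to the list chosen.

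**Step 4: chance of use.** Per endpoint, 0.20 × 96 = 19.2, so 20 missing values are needed. Counted by subjects, 0.20 × 48 = 9.6, so 10. At 5% drop-out, 0.05 × 48 = 2.4 subjects; with one period lost each, 2.4/96 = 2.5%.

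**Step 5: what the removed subjects could change.** With 20 one-period subjects, 28 pairs remain and the primary SE is 0.5545 × sqrt(2/28) = 0.148. The mixed model on all data gives mean SEs of 0.129 / 0.134 / 0.139 and moves the log ratio by 0.055 / 0.048 / 0.040 on average. With 10 one-period subjects, and between-subject SD equal to within-subject SD, the SE falls only from 0.127 to 0.124. The largest shift in the ratio over 30 such runs was about 8%.

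**Step 6: non-random loss.** True ratio 1.00, 1,500 runs per SD; results in the order 0.3 / 0.5 / 0.8.

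| Loss mechanism | Complete pairs | All data |
|---|---|---|
| (i) 14 lowest period-1 CHTP values (CHTP-first sequence) lose period 2; 6 random in the other sequence | 1.24 / 1.21 / 1.15 | 1.00 / 1.00 / 0.99 |
| (ii) 20 lowest CHTP values are themselves lost | 1.377 / 1.319 / 1.236 | 1.485 / 1.520 / 1.459 |
| (iii) 14 lowest period-2 values (CHTP-first) are lost; 6 random in the other sequence | 0.801 / 0.827 / 0.864 | 0.762 / 0.757 / 0.779 |

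The all-data model removes the bias in (i), where loss depends on observed values. It is further from 1.00 in (ii) and (iii), where loss depends on the unobserved value.

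**The case against.** The wording of 11.6.3 is plural across parameters, and a 20% cut has little meaning when an endpoint offers only 0, 50 or 100%. A pooled count may therefore be intended. That stands, so a reader should not infer that the check always reproduces the primary ratio; this is shown only for the per-endpoint count. The pooled count does not rescue the check: one-period subjects still go, and complete Cmax pairs can go with them.

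If only attended periods were counted, a one-period subject could be 0% missing and stay in. The SAP does not say this, and such a count would not register an absent period as missing. The possibility supports stating the denominator.

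A reader might infer that no planned analysis uses one-period subjects. The documents do not support that. Section 11.6.1 has no both-products restriction, and these subjects enter its LS means. In simulation they moved the log LS mean by 0.04 to 0.05 on average with 10 such subjects, and by 0.06 to 0.09 with 20. Only the contrast ignores them.

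It is also tempting to say that, on a pooled count, a subject missing only AUC(0-last) in one period would stay and add information. Under 7.1.2, losing it means losing the other AUCs too, and the share exceeds 20% on every list.

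The exclusion may be deliberate, since 11.6.2.1 limits secondary PK comparisons to subjects with both products. That would be defensible for a paired analysis, but it does not fit the purpose stated for this one.

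**Conclusion.** The point holds. The exclusion in 11.6.3 conflicts with the purpose in 11.6.1. On a per-endpoint count the check cannot differ from the primary ratio; on a pooled count it can lose complete Cmax pairs, and its analysed set depends on an unstated list. This rests on counting both planned periods and, for the withdrawal figures, on treating NC as missing.

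The impact is minor. The primary estimate and CI are unaffected, and the analysis is supportive, conditional and unlikely to run at the assumed drop-out. The 20-of-48 results describe a severe case on one reading of the trigger. Nothing here shows that the primary analysis is biased, or that the all-data model would correct it. The value of that model is that it can differ from the primary result.

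**What to change.** In 11.6.3:
- Delete the subject-level 20% exclusion.
- Fit the mixed model, in the form coded in 11.6.2.3.2, to all available log values of Cmax and, separately, of AUC(0-last), including subjects with one evaluable period.
- Count the 20% trigger per endpoint as missing over planned values.
- Report the result beside the primary ratio as a sensitivity comparison that is valid when loss depends on observed values, not as a correction.

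Section 11.6.2.1 refers its secondary parameters to the same analysis; one sentence should say whether they are covered and, if so, that its both-products restriction does not apply to this model.

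The cost is about three sentences. The code form exists, and neither data collection nor the primary analysis changes. The downside is that the all-data model can be more biased than complete pairs when loss depends on the unobserved value itself, and the report should say so.

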11.6.2 Secondary Analyses

11.6.2.1 Pharmacokinetics

The secondary PK parameters ($AUC_{(0-12)}$, $AUC_{(0-t^*)}$, $AUC_{(0-\infty)}$, $\%AUC_{extrap}$, t_{last} , t_{max} , λ_z and $t_{1/2}$) will be listed and summarized as described in Section 11.1 “General Considerations” and subsections. In addition plots of the data versus product will be provided.

The nicotine plasma concentrations will be summarized in a similar manner to the PK parameters but will also be split out by sample time point. Geometric mean (95% CI) profiles, spaghetti plots of all subjects and individual PK profiles for each subject will also be presented.

PK parameter and plasma concentration data will also be listed along with the details of the actual times after T_0 .

Only subjects in the PK population who provide evaluable data for both the CHTP 1.1 M and mCC products will be included in the following analyses.

- The secondary analysis of $AUC_{(0-12)}$, $AUC_{(0-\infty)}$, $AUC_{(0-t)}$ and $t_{1/2}$ will be performed on the natural log-transformed parameters using the same ANOVA model as used for the primary analysis. (Section 11.6.1 “Primary Analyses”).
- The analysis of t_{max} will be performed by calculating the difference for each subject (CHTP 1.1 M - mCC) and obtaining the Hodges-Lehmann (**Hodges and Lehmann, 1963**) 95% CI estimates. The median t_{max} for each product and the median difference between the products along with the 95% CI will be presented in the tables.

Supportive analysis will be performed as described in Section 11.6.3 "Supportive/Sensitivity Analysis" in order to evaluate the sensitivity of CHTP 1.1 M effect estimates to methods used for missing data by means of a mixed model approach, should there be 20% or more missing parameter PK model.

TFL number	Title
TABLES	
15.2.4.1	Analysis of Secondary Pharmacokinetic Parameters of Nicotine – PK Population
15.2.4.4	Descriptive Statistics of Pharmacokinetic Parameters of Nicotine – PK Population
15.2.4.4.1	Descriptive Statistics of Pharmacokinetic Parameters of Nicotine by Sex – PK Population
15.2.4.4.2	Descriptive Statistics of Pharmacokinetic Parameters of Nicotine by Nicotine Level – PK Population
15.2.4.5	Descriptive Statistics of Plasma Nicotine Concentrations (ng/mL) – PK Population
15.2.4.5.1	Descriptive Statistics of Plasma Nicotine Concentrations (ng/mL) by Sex – PK Population
15.2.4.5.2	Descriptive Statistics of Plasma Nicotine Concentrations (ng/mL) by Nicotine Level – PK Population

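### SAP 11.6.3 sends the missing-sample sensitivity analysis of tmax to the log-scale ANOVA of 11.6.1, so its result will not be on the scale of the planned Hodges-Lehmann analysis in 11.6.2.1

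*SAP*

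**What the plan says.** Section 11.6.3 introduces the three missing-sample analyses with "Sensitivity analysis will be conducted following the model described in 11.6.1". Item 2 concerns a missing sample before 1 h after exposure and states that "the parameters C_{max} and t_{max} will, as well as being analysed and reported as planned, have a sensitivity analysis excluding those subjects" with such a gap. Section 11.1.5 gives the same exclusion rule without naming a method.

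The 11.6.1 analysis "will be performed on the natural log-transformed parameters using an analysis of variance (ANOVA) model with terms for sequence, subject nested within sequence, period and" a fourth term, for the product used. Its output is defined as follows: "LS means for each product will be back-transformed by exponentiation and will be tabulated together with the ratio (CHTP 1.1 M : mCC) and 95% CI".

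Section 11.6.2.1 applies that same ANOVA to the secondary AUCs and the half-life but treats tmax in a separate bullet. The tmax analysis "will be performed by calculating the difference for each subject (CHTP 1.1 M - mCC) and obtaining the Hodges-Lehmann" 95% CI, and the median tmax "for each product and the median difference between the products along with the 95% CI will be presented in the tables".

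Later in 11.6.3, if imputing missing seconds moves the median tmax for CHTP 1.1 M by more than 5%, "a supportive analysis will be conducted by repeating the analyses described in Section 11.6.1 “Primary Analyses” and 11.6.2.1". That check includes tmax and cites both sections.

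**The concern.** A sensitivity analysis is informative when it changes one thing and leaves the rest alone. Here the intended change is the removal of subjects with a missing early sample. For tmax the lead sentence also replaces a rank-based paired analysis with a parametric ANOVA, and a difference in time with a ratio. The SAP plans no log-scale ANOVA of tmax on the full set, so there is nothing on the same footing to compare with.

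tmax is the only endpoint of secondary objective 2 (section 5.2). It is also one of the three PK parameters in the table that section 12.5 lists for possible registry reporting. Samples before 1 h are the ones most likely to determine it, so this is the sensitivity check a reader would want to be clean.

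**Working it through.** This is a comparison of text; the SAP gives no figure on this point to reproduce.

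**Step 1: planned method against sensitivity method**

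| Parameter in the 11.6.3 list | Planned analysis | Sensitivity analysis as written | Same method and scale? |
|---|---|---|---|
| AUC(0-last), item 1 | log ANOVA, ratio (11.6.1) | log ANOVA, ratio | yes |
| Cmax, item 2 | log ANOVA, ratio (11.6.1) | log ANOVA, ratio | yes |
| tmax, item 2 | paired difference, Hodges-Lehmann (11.6.2.1) | log ANOVA, ratio | **no** |
| AUC in item 3 (printed AUC0-t) | log ANOVA, ratio (11.6.2.1, by reference to 11.6.1) | log ANOVA, ratio | yes |

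Only tmax is mismatched. The ANOVA also adjusts for period, which the paired difference described in 11.6.2.1 does not.

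**Step 2: does any other text redirect tmax?** Section 11.1.5 names no method. The zero-second check cites 11.6.1 and 11.6.2.1 together, but it is a separate analysis with its own trigger. Nothing else in the SAP sends the missing-sample tmax analysis to 11.6.2.1.

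**Step 3: is the difference only one of units?** No. A constructed example with assumed values shows this. Take ten subjects: five with tmax of 2 min (CHTP 1.1 M) and 8 min (mCC), and five with 30 min and 15 min.

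- The differences are −6 (five times) and +15 (five times). The 10 × 11 / 2 = 55 pairwise averages are 15 at −6, 25 at (−6 + 15)/2 = 4.5, and 15 at +15. The median is the 28th, so Hodges-Lehmann gives +4.5 min, with CHTP 1.1 M later.
- The geometric mean ratio is √[(2/8) × (30/15)] = √0.5 = 0.71, with CHTP 1.1 M earlier.

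Nobody has been excluded, yet the two summaries point in opposite directions. The set was built to show that this is possible and says nothing about how often it would happen.

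**Step 4: could the rule be triggered?** Table 11 schedules eight samples after T0 and before 1 h (2, 4, 6, 8, 10, 15, 30 and 45 min). Two periods give 16 per subject, and 48 subjects give 16 × 48 = 768. The SAP states no missing rate, so assume independent misses with probability p per sample and all 48 subjects completing both periods:

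- chance of at least one miss = 1 − (1 − p)^768
- expected subjects excluded = 48 × [1 − (1 − p)^16]

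| Assumed p | Chance of at least one miss | Expected subjects excluded |
|---|---|---|
| 0.1% | 54% | 0.8 |
| 0.5% | 98% | 3.7 |
| 1% | above 99% | 7.1 |

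Across this assumed range the trigger is realistic, and the number excluded runs from about one to about seven.

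**The case against.** The strongest reply is that this is an incomplete cross-reference and the intent can be recovered. Items 1 to 3 describe the change as an exclusion of subjects, 11.6.2.1 deliberately sets tmax apart from the ANOVA parameters, and the zero-second check cites both sections. A careful programmer would probably guess Hodges-Lehmann. That is a fair reading of intent, but it does not remove the problem. The written rule names 11.6.1 alone. Following it gives a non-comparable result, and not following it departs from the described analysis, which section 3 requires the CSR to report.

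The second reply is about reach, and it stands in full. The analysis runs only if an early sample is missing, tmax is secondary, section 5.4.1 states that no hypothesis is tested, and section 11.1.7 states that no claim rests on individual intervals.

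A reader might infer that the check can show nothing at all about the missing samples. The documents do not support that. The direction of the product effect can still be compared roughly, and 11.6.2.1 lists individual PK parameters and concentrations with actual times, so affected subjects can be inspected. A reader might also take the constructed example as a forecast of reversed conclusions. It is not one, because the SAP gives no tmax distribution from which to estimate how often the methods would disagree.

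**Conclusion.** The point holds as a defect in a stated rule. As written, the tmax result under item 2 would differ from the planned result in method, scale and subjects together, so a discrepancy could not be cleanly attributed to the missing samples. It should be corrected, but it is modest: one conditional sensitivity analysis of one secondary endpoint.

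The planned tmax analysis is unaffected, as are the primary analyses and the sensitivity analyses of Cmax, AUC(0-last) and the item 3 AUC. No trial figure changes, and no numerical bias is claimed. The conclusion rests on reading the lead sentence as governing all three items, which is how it is laid out. The assumed missing rates bear only on whether the analysis is likely to be run.

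**What to change.** Amend the lead sentence in 11.6.3 so that the 11.6.1 model applies to Cmax, AUC(0-last) and the AUC in item 3, and the Hodges-Lehmann method of 11.6.2.1 applies to tmax. Report tmax in the missing-concentrations sensitivity table (apparently 15.2.4.2.3) as a difference in time with its 95% CI, in the same unit as Table 15.2.4.1. Section 11.6.2.1 does not state that unit, so it should be named in the table shell. The item 3 label should be checked in the same edit, since it is printed as AUC0-t.

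The cost is one clause in the SAP and a rerun of the planned tmax program on the reduced set. No new method is needed, and nothing is lost by the change.
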